7.6.8 PATIENT REPORTED OUTCOMES

Patient self-reported measures will be assessed at baseline, Days 28 and 56, and 6 months post-randomization using the MD Anderson Symptom Inventory (MDASI) and selected PROMIS subscales. The core symptom severity and mean interference subscales of the MDASI and the PROMIS domains will be scored according to the recommendations of the developers.

For each subscale/domain considered, scores at baseline, Days 28 and 56, and 6 months post-randomization will be described in the ITT population by treatment arm using the

sample mean, median, range, and quartiles in tables of summary statistics and displayed graphically using box plots. Linear regression models will be used to compare trajectories in scores over time between treatment arms while adjusting for baseline score; model effects will include treatment assignment, baseline score, and post-randomization assessment time (Day 28, Day 56, or 6 months).

Provided that at least 10 adolescent participants are enrolled, separate analyses of patient reported outcomes will be conducted for adolescents and adults. Otherwise, their data will be aggregated for one common analysis.

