1.3.1 Risk Stratification by Clinical Grading using Onset Organ Severity

In 1990, Weisdorf et al. identified in multivariate analyses that overall stage score (sum of each acute GVHD organ stage 0-4, plus 1 point for upper GI, for a maximum score of 13) was strongly associated with likelihood of CR¹⁷. Based upon this initial observation that single organ involvement was more likely to achieve a CR than multi-organ involvement, the GVHD Risk Score was subsequently developed by the Minnesota group¹⁸. Multivariate analysis of the outcomes of 864 consecutive patients from 1990-2007 yielded the following high-risk organ stages: skin stage 4, lower gastrointestinal stage 3/4, liver stage 3/4, or skin stage 3 plus lower gastrointestinal or liver stage ≥ 2 GVHD.

The GVHD Risk Score has recently been refined using data from multiple centers with a total of 1,723 patients used in modeling – the largest acute GVHD cohort analyzed for their characteristics and outcomes to date¹⁹. Developed using clinical grouping and recursive partitioning, this new Risk Score (<http://z.umn.edu/MNAcuteGVHDRiskScore>) [referred to as Minnesota (MN) Risk Scores] can classify patients into high-risk (HR) or standard risk at the onset of acute GVHD symptoms. In this model, 84% of patients are classified as standard risk, defined as single organ involvement (stage 1-3 skin or stage 1-2 GI) or two organ involvement (stage 1-3 skin plus stage 1 GI; or stage 1-3 skin plus stage 1-4 liver), with a Day 28 CR/PR rate of 69% (Figure 1-1). All others are considered HR, with a Day 28 CR/PR rate of 43%. This model can be used in real time at the time of acute GVHD diagnosis, making it practical for stratification in clinical trials. Similarly, this model predicted for 6-month NRM (Standard risk 22% vs High risk 44%, p-0.001).

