5.8.3 Immune Subsets

The changes in peripheral blood ratios of T regulatory to T effector (Treg/Teff) cells, Natural Killer (NK) cells and other cellular immune subsets from baseline to Days 16, 28, and 56 post-treatment initiation will be summarized using descriptive statistics at each time point and compared between treatment groups using Mann-Whitney nonparametric tests. Select immune subsets may also be analyzed using a linear mixed model adjusting for baseline value, time and treatment, as well as a treatment by time interaction term.

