5.8.8 Patient-Reported Outcomes

Participant self-reported measures for both adolescents and adults will be assessed at baseline, Days 28, 56 and 180 post-randomization by MDASI, and selected PROMIS subscales for gastrointestinal symptoms, physical function and satisfaction with participation in social roles. These instruments will be scored according to the recommendations of the developers. The scores will be examined using the medians, means, ranges, and standard deviations. Linear regression models for the Day 28, Day 56 and 6-month score adjusting for baseline score and other covariates will be used to explore differences between treatment arms and changes in outcomes over time. Provided there is sufficient data, separate analyses will be conducted for adolescent and adult patients. Otherwise, their data will be combined/aggregated.

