4.3 SIMULATION STUDY

A simulation study was conducted to evaluate the power provided by a logistic mixed model in this sequential design. Randomized treatment assignments were generated for each simulated trial using stratified randomized block design at a 1:1 ratio with permuted blocks of size 6, with center accrual numbers obtained from those observed in participating centers of the BMT CTN 1501 study. Centers with fewer than 10 patients were combined, resulting in 6 center-groups of size 23, 19, 17, 15, 14, and 48. We assumed these groups' random effects are a random sample from a zero-mean normal distribution. Additionally, we estimated that 65% of the patients would be classified as Refined Minnesota high risk, with GVHD risk (MN high vs. standard) included as a fixed effect in the logistic model for all simulations. We considered possible effect sizes of 10%, 15%, 20%, and 25% and standard deviations for the random effects of 0.05, 0.60, and 1.00, with 1000 replicated trials simulated for each scenario.

Simulation results in Table 5 indicate that, in the near absence of a random effect (i.e., when the standard deviation of the random effect is close to zero), the statistical power is at least 94.2% to detect an odds ratio of 3.0, corresponding to an effect size of 25%. Further, when the random effect is present (standard deviation of 0.6 or 1.0), statistical power is at least 92% and 90% to detect an odds ratio of 3.0. For any other given effect size, the power levels are similar regardless of the variability of the random effects. These results support the ability of the logistic mixed model to provide at least 86% power in this group sequential design.

Table 5: Empirical Power for Logistic Mixed Model (1000 simulations per scenario)

Effect Size (AAT vs. PTM)		Power (%)		
		Standard Deviation of Random Effects		
Difference in Day 28 CR/PR		Odds Ratio	0.05	0.60
10%		1.500	25.5	24.2
15%		1.857	53.8	51.3
20%		2.500	85.0	83.4
25%		3.000	94.2	92.9
				90.1

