7 STATISTICAL METHODOLOGY

7.1 GENERAL GUIDELINES

Counts and percentages will be used to describe categorical variables, while the number of subjects (N), median, mean, standard deviation, interquartile range and range will be used to summarize continuous variables.

The study day for most efficacy and safety assessments will be computed in reference to the date of randomization, with the date of randomization defined as Study Day 0 for each patient. For all assessments, the (Study) Day will be calculated as (assessment date – randomization date). Unless otherwise specified, the visit window will be defined similarly to those specified in the protocol with the target day calculated in reference to the date of randomization. For outcomes where data are summarized in reference to a different date, such as treatment initiation, the assessment time point is clarified explicitly.

For each patient-reported outcome, the baseline value is defined as the outcome score assessed at the Pre-Therapy visit on the schedule of assessments (**Section 2.2**). For all other variables, unless otherwise specified, the baseline value is defined as the last available measurement prior to the first infusion of study drug if the measurement time was collected and the last available measurement before or on the date of the first infusion of study drug if the measurement time was not collected.

Hypothesis testing for the primary endpoint's analysis is one-sided, evaluating the superiority of AAT to PTM for Day 28 overall response, at a 2.5% significance level. The testing for secondary endpoints will be two-sided at a 5% significance level and is equivalent to assessment by two one-sided tests, each at a 2.5% level. Testing of exploratory endpoints will be two-sided at a 1% significance level. **Table 14** summarizes the endpoints to be analyzed for each analysis population.

A hierarchical testing procedure will be employed to ensure control of the familywise type I error rate at a one-sided, 2.5% level when evaluating the primary and key secondary endpoints of interest. A gatekeeping approach will be used with the following tests of superiority of AAT to PTM for the corresponding endpoints:

1. Overall Response at Day 28: The Wald test from the primary analysis as specified in **Section 7.4.3.1** (one-sided at 2.5% level)

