2. Duration of Response, Primary Definition: The log-rank test for comparing the DOR from Day 28 to 12 months post-randomization from the primary analysis as specified in **Section 7.5.1** (two-sided at 5% level)
3. Duration of Response, Supplementary Definition: The log-rank test for comparing the DOR from Day 28 to 12 months post-randomization from the supplementary analysis as specified in **Section 7.5.1** (two-sided at 5% level)
4. Non-relapse Mortality: The Gray's test for comparing the cumulative incidence of NRM from randomization to 12 months post-randomization as specified in **Section 7.5.2** (two-sided at 5% level)
5. Overall Survival: The log-rank test for comparing the OS from randomization to 12 months post-randomization from the primary analysis as specified in **Section 7.5.3** (two-sided at 5% level)

6. Progression-free Survival: The log-rank test for comparing the PFS from randomization to 12 months post-randomization from the primary analysis as specified in **Section 7.5.4** (two-sided at 5% level)
7. GVHD-free Survival at Day 56: The Wald test from the logistic mixed model as specified in **Section 7.5.5** (two-sided at 5% level)

The gatekeeping procedure evaluates the endpoints sequentially in the order displayed and ends if the one-sided test or two-sided test for an endpoint fails to find a significant result showing superiority of AAT to PTM, precluding further testing of any remaining endpoints in the hierarchy. This strategy ensures control of the one-sided familywise type I error rate at 2.5% and permits claims of confirmatory benefit for any endpoint(s) where superiority of AAT is demonstrated. Any hypothesis testing performed outside the hierarchy is deemed descriptive in this study.

Analyses for several endpoints involve adjustment for center effects through regression modeling. Because the average number of patients enrolled per center is expected to be small ($136/25 \approx 5.5$), centers will be combined into center-groups for these analyses to ensure the stability of the models. This will be done by including the top 5 enrolling centers each as a separate group and combining all other centers into a sixth catchall group.

All efficacy analyses will be conducted using the ITT population unless otherwise specified.

Table 14: Endpoints for Analysis Under Each Analysis Population

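### SAP 7.6.8 sets out to compare PRO trajectories, but its listed model has no treatment-by-time term and no stated within-patient covariance

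*SAP*

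**What the plan says.** SAP 7.6.8 schedules the MDASI and PROMIS scores at baseline, Day 28, Day 56 and 6 months. It promises by-arm summary tables and box plots at each time point, and then a model: "Linear regression models will be used to compare trajectories in scores over time between treatment arms while adjusting for baseline score". The terms follow: "model effects will include treatment assignment, baseline score, and post-randomization assessment time (Day 28, Day 56, or 6 months"). No interaction, patient effect, covariance structure or robust variance is mentioned, and the section names no specific test or interval.

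Protocol 5.8.8 plans linear regression for the Day 28, Day 56 and 6-month score, adjusted for baseline and other covariates, which "will be used to explore differences between treatment arms and changes in outcomes over time".

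SAP 7.1 sets the level and the status of such tests: "Testing of exploratory endpoints will be two-sided at a 1% significance level", and "Any hypothesis testing performed outside the hierarchy is deemed descriptive in this study".

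For immune subsets, another repeated exploratory measure, protocol 5.8.3 allows for selected subsets a "linear mixed model adjusting for baseline value, time and treatment, as well as a treatment by time interaction term".

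**The concern.** There are two separate gaps.

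The first follows from the text alone. Comparing trajectories means asking whether the difference between arms changes over time. A model with main effects only cannot ask that, because its treatment coefficient is the same at every visit. An effect confined to one visit is diluted, and opposite effects at different visits cancel. This matters for the stated objective, which is change from baseline to each of three time points. It also matters because study drug ends at Day 28 for non-responders and by Day 56 for responders, so there is no reason to expect an equal effect at 6 months.

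The second is conditional. If the visits share one model, each patient contributes up to three correlated scores. Standard errors computed as if those scores were independent are too small, and tests at the 1% level would reject too often.

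**Working it through.** **Inputs from the documents.** 136 patients randomized 1:1; three post-baseline visits; two-sided 1% level for exploratory endpoints (SAP 7.1).

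**Assumed inputs, not in the documents.** Residual within-patient correlation ρ of 0.3-0.7, the same for every pair of visits; the share of scores observed at Day 28 / Day 56 / 6 months; non-informative missingness.

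**1. Dilution.** In a least-squares model with a common treatment effect, an effect present at one visit only is estimated at roughly that visit's share of all observed scores.

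| Completion (%) | Day 28-only effect shown at | 6-month-only effect shown at |
|---|---|---|
| 100/100/100 | 1/3 = 33% | 1/3 = 33% |
| 85/75/60 | 85/220 = 39% | 60/220 = 27% |
| 75/60/40 | 75/175 = 43% | 40/175 = 23% |

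Simulation with a true effect of 0.6 SD at one visit and ρ = 0.5 gave estimates of 0.198/0.230/0.257 for Day 28-only (33/38/43%) and 0.198/0.166/0.133 for 6-month-only (33/28/22%).

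**2. Size of the test under independent-error least squares.** True size = 2 × (1 − Φ(2.576 / √(1 + kρ))), where k = Σm(m − 1) / Σm and m is the number of scores a patient contributes.

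With ρ = 0 the formula returns exactly the plan's 1%. Simulation (8,000 fits per scenario) returned 0.9-1.2%.

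Complete data: k = 2.

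Monotone dropout, 85/75/60%: 60% of patients give three scores, 15% two and 10% one, so k = (0.60 × 6 + 0.15 × 2) / 2.20 = 1.77.

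Monotone dropout, 75/60/40%: k = (0.40 × 6 + 0.20 × 2) / 1.75 = 1.60.

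Independent gaps with completion a, b, c: k = 2(ab + ac + bc) / (a + b + c). This gives 1.45 for 85/75/60% and 0.87 for 60/45/30%.

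| Pattern | ρ = 0.3 | ρ = 0.5 | ρ = 0.7 |
|---|---|---|---|
| Complete | 4.2% | 6.9% | 9.6% |
| Monotone 85/75/60 | 3.7% | 6.1% | 8.5% |
| Monotone 75/60/40 | 3.4% | 5.5% | 7.7% |
| Independent gaps 85/75/60 | 3.2% | 5.0% | 7.0% |
| Independent gaps 60/45/30 | 2.2% | 3.1% | 4.2% |

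Simulations agree within simulation error. At ρ = 0.1-0.2 with monotone dropout, simulated size was 1.6-2.7%. With patient-clustered standard errors and 136 patients, the same simulated data rejected 0.7-1.3% of the time, so the ignored correlation is the cause.

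**3. Is missing 6-month data plausible?** Protocol 1.3.1 reports that "this model predicted for 6-month NRM (Standard risk 22% vs High risk 44%, p-0.001"). The 22% covers all Minnesota standard-risk patients, whereas this trial enrols only two subsets of them. Protocol Table 1-1 gives 6-month NRM for those subsets: 29% (n = 14), 33% (19), 44% (9) and 30% (30). Weighted by n: (14 × 29 + 19 × 33 + 9 × 44 + 30 × 30) / 72 = 2329/72 = 32%.

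For the case mix, SAP 4.3 states: "we estimated that 65% of the patients would be classified as Refined Minnesota high risk". Protocol 5.3.2.1 puts the high-risk share at 35%. Using both:

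- 0.65 × 44% + 0.35 × 32.3% = 39.9%
- 0.35 × 44% + 0.65 × 32.3% = 36.4%

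History therefore suggests roughly 36-40% non-relapse deaths by 6 months, before relapse deaths, missed forms and the language limits on the instruments.

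**The case against.** The strongest reply is that the visits may not be pooled at all. Protocol 5.8.8 can be read as one regression per visit, and SAP 7.11 says that the exploratory significance level is the only change from the protocol analysis. On that reading the visit-specific differences are already planned and no size inflation arises. But assessment time can be an effect only if visits share a model, so the SAP text favours pooling. The documents leave this open, and that is itself worth settling. Protocol 5.8.8 also speaks of change over time, so pooling is not in itself a departure from the protocol.

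A reader might infer that the SAP commits to a test running at several times its nominal level. The documents do not support that. SAP 7.6.8 names no error structure and no test, and the inflation also depends on correlation and completion values that the documents do not give. The SAP does say mixed model where it wants random effects (7.4.1, 7.5.5) and writes out an interaction where it wants one (7.6.5). This makes the plain reading natural, but not certain.

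A reader might also take protocol 5.8.3 as a standard that 7.6.8 fails. It is not one. The mixed model there is optional and for selected subsets, and the matching SAP section (7.6.3) lists only summaries and rank tests. It shows only that the needed terms were familiar to the authors.

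Finally, the by-visit tables and box plots would still show a single-visit effect, and SAP 7.10.2 already tabulates missed visits by arm. Both points stand and limit the consequence.

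**Conclusion.** The gap is real and its severity is low. That the listed effects yield only a time-averaged difference follows from the text. The dilution to about 33-43% (Day 28 only) or 22-33% (6 months only) depends on assumed completion.

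The size inflation is conditional on independent-error least squares, residual correlation 0.3-0.7 and missing scores, all assumed. Under those conditions a nominal 1% test runs at about 2-9%: roughly 3-9% with monotone dropout and 2-7% with independent gaps. The 36-40% historical mortality mix makes substantial 6-month missingness plausible. It comes from past cohorts, so it is a guide and not a ceiling on completion in this trial.

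It would be wrong to infer a threat to the trial's conclusions. PROs are exploratory and lie outside the testing hierarchy, so no confirmatory claim is affected.

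**What to change.** In SAP 7.6.8, choose one of the following and say so:

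- A repeated-measures mixed model with treatment, visit, treatment-by-visit and baseline score, a named within-patient covariance (for example unstructured) and a stated simpler fallback.
- A baseline-adjusted ANCOVA at each visit.

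In either case report the treatment difference at each visit, and state that scores come only from patients alive and completing the form. If only an average is wanted, call it a time-averaged difference and still name the covariance. For an adolescent subset near the 10-participant threshold, use descriptive summaries: with 10 patients and complete data, the per-visit 95% half-width is about 2.365 × √(4/10) = 1.5 residual SD.

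The cost is small. SAP section 1 allows revision before database hard lock, and the named software handles either model. There will be three estimates per subscale instead of one, with wider intervals. With complete data a per-visit standard error is √(3/(1 + 2ρ)) times that of a correctly computed average, which is 1.37 at ρ = 0.3 and 1.12 at ρ = 0.7. Three 1% tests per subscale carry a chance of at least one false rejection of 1 − 0.99³ = 3.0% if independent and about 2.4% at correlation 0.7. Report them as descriptive, or use one joint test.

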7.7 INTERIM ANALYSES

7.7.1 FUTILITY ANALYSIS OF PRIMARY ENDPOINT

This trial includes one formal interim analysis for futility, to occur once 76 patients are evaluable for the primary endpoint. The existence of a futility signal will be determined as specified in Section 7.4.1. Note that this is non-binding futility stopping rule, in that the type I error rate will not exceed 2.5% if the DSMB chooses not to stop the trial in the presence of a futility signal.

7.7.2 ANALYSIS FOR 6-MONTH CLINICAL STUDY REPORT

To expedite the evaluation of the primary endpoint and to support a potential regulatory submission, a clinical study report will be drafted once all enrolled participants complete 6 months of follow-up in the study. This report will include efficacy, safety, and PK data collected through the data cut-off date. Analysis included in this report will consist of descriptive statistics on baseline characteristics and outcomes as well as formal treatment comparison for the primary endpoint Day 28 overall response via hypothesis testing. The p value from the test of superiority of AAT to PTM will be calculated via a logistic mixed model for GVHD-free survival at Day 56. This p value is considered descriptive in the 6-month report and will not be formally evaluated for efficacy of AAT until all the testing entailed in the hierarchical testing procedure is completed at the end of the study. The analysis will be performed using the statistical methods detailed in Sections 7.4-7.6.

A detailed account of which TLFs will be included in the 6-month clinical study report is provided in the supplementary TLF shell document for this SAP.

7.8 SAFETY ANALYSIS

7.8.1 DATA AND SAFETY MONITORING BOARD

The policies and composition of the Data and Safety Monitoring Board (DSMB) are described in the BMT CTN MOP. The DSMB performs a review of key efficacy and safety data at least once a year at regularly scheduled meetings. Additional reviews may occur on an ad-hoc basis by request of the DSMB. The content of the data reports provided for DSMB reviews is not specified by this SAP.

7.8.2 STATISTICAL MONITORING RULES

The rate of non-relapse mortality occurring by Day 56 will be monitored monthly for each treatment arm. If either rate significantly exceeds pre-set thresholds, the NHLBI will be notified so that the DSMB can be advised. These stopping guidelines serve as triggers for consultation with the DSMB for guidance and are not formal “stopping rules” that would mandate automatic closure of study enrollment. The monitoring scheme is detailed in section 5.3.4 of the study protocol.

7.8.3 SAFETY EVENT SUMMARIES FOR ANALYSIS REPORTS

All safety analyses will be conducted using the safety population. All AEs and SAEs reported on the study will be categorized by MedDRA preferred terms using MedDRA version 23.0 and higher. The number of each type of event and number of patients affected will be described during two study periods: from randomization until 30 days following the last dose of study drug (AAT/PTM), and from 30 days following the last dose until 12 months post-randomization. These events will be reported using the safety analysis population.

In addition, AEs and SAEs will be described in the same manner for the set of patients who received Ruxolitinib or other approved next-line therapy and those who did not. Causes of death for expired participants will be tabulated.

